#### **4.2.3 Number of subjects required to be included in the study**

Enrollment will include at least 20 patients undergoing lung transplant. The subjects will be evaluated with the historic controls (50).

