### **4.3 OBJECTIVES**

#### **4.3.1 Primary Objective**

Demonstrate safety and effectiveness of the amiodarone hydrogel application during lung transplantation in preventing atrial arrhythmias during index hospital stay.

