### **4.5 INCLUSION AND EXCLUSION CRITERIA**

A subject, who meets all of the inclusion criteria, and none of the exclusion criteria, is eligible to participate in this study.

All subjects enrolled in the clinical study (including those withdrawn from the clinical study or lost to follow-up) will be accounted for and documented, assigning an identification code linked to their names, alternative identification or contact information.

A log with enrollment information will be kept up to date throughout the clinical study by the principal investigator or his/her authorized designee. To ensure subject privacy and confidentiality of data this log must be maintained throughout the clinical study at the clinical site.

To participate in this clinical study, the subject must meet all of the following inclusion criteria and none of the exclusion criteria:

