#### 6.2.4 Prior to lung transplant

When a consented subject is informed that they are scheduled for a lung transplant, the study team will review their medical record to confirm they are still eligible to participate in the study. If they meet any of the exclusion criteria since the initial consent was signed, they will be considered a screen failure and will not undergo the study procedure.

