### **6.4 CRITERIA AND PROCEDURES FOR SUBJECT WITHDRAWAL OR DISCONTINUATION**

Subjects must be informed about their right to withdraw from the study at any time and for any reason without sanction, penalty or loss of benefits to which the subject is otherwise entitled and withdrawal from the study will not jeopardize their future medical care or relationship with the investigator. Subjects will be asked to specify the reason for the termination, but have the right not to answer.

The investigator may decide to withdraw a subject from the study at any time with reasonable rationale. The subject's future care will not be influenced by a decision, voluntary or otherwise, to withdraw from the study. All reasonable efforts should be made to retain the subject in the clinical study until completion of the study.

Reasons for subject's withdrawal include, but are not limited to:

- Subject refuses to continue participating in the study
- Subject does not meet the inclusion/exclusion criteria and does not require additional follow-up for safety reasons.
- Subject is deceased (cause must be documented)
- Subject's non-compliance
- Subject's participation is terminated by the PI or investigator, although the subject consented, since participation is no longer medically appropriate
- Subject is 'lost to follow up': Subject does not adhere to the scheduled follow up visits but has not explicitly requested to be withdrawn from the clinical study. Site personnel should at all times make

all reasonable efforts to locate and communicate with the subject in order to achieve subject compliance to the scheduled follow up visits:

1. A subject will be considered 'Lost to Follow Up' after a minimum of 2 phone calls of a physician or delegate at the investigational site to the subject or contact. These 2 phone calls need to be documented in the subject's hospital records.

Note: If a subject misses one or more of the scheduled follow up visits (inclusive of the assigned visit windows), this will be considered as a missed visit. The subject may therefore still return for subsequent visits and will not be excluded from the study.

If a subject withdraws from the clinical study, the site will record the subject's reasons for withdrawal (if available), on a Withdrawal CRF.

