## 14.0 STATISTICAL CONSIDERATIONS

### 14.1 STATISTICAL DESIGN, HYPOTHESES, METHOD AND ANALYTICAL PROCEDURES

This clinical study will provide data to support the safety, preliminary efficacy, and performance of the use of the Amiodarone hydrogel in preventing atrial arrhythmia during lung transplantation. The study has a treatment arm and a control arm. The control arm is the historic controls and will use the previously treated lung transplant patients at the facility. The treatment arm will use investigational amiodarone hydrogel. The study sample size calculation is based on typical regulatory criteria for a feasibility study to assess for safety and preliminary effectiveness hence it is not based on a power analysis to show statistically significant difference between the groups. However, the reported rate of early atrial fibrillation post lung transplantation is approximately 30% and assuming that the use of amiodarone gel will result in prevention of atrial fibrillation in 90% patients a sample size of 20 in each arm may have sufficient power to answer the question of preliminary effectiveness and safety.

Endpoint analysis will be on “as-treated” basis as historical control data will be used. Patients who will dropout or withdraw from the study before reaching the primary end-point will be excluded from the study and replaced by new enrollees to have at least 20 patients enrolled the study arm. The primary end-point analysis will be based on the study groups as per the protocol (treatment group vs. control groups). Subjects, who withdraw consent, will not be included in analyses.

All clinically relevant baseline and follow up variables will be tabulated. Means, medians, proportions and 95% confidence intervals will be reported. Comparisons of data collected at baseline and at follow-up will be analyzed as follows: categorical variables will be tested using contingency tables analyses (exact or chi-square approximations), and continuous variables will be tested using unpaired Student’s t-test or Wilcoxon rank-sum test, depending on variable distribution. The post-transplant AFIB was evaluated between study and control groups for overall occurrence, AFIB lasting < 24 hours and AFIB lasting > 24 hours. All the data were analyzed using SAS 9.4 software (SAS Inc., Cary, NC).

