## Post-operative Information

ICU Length of Stay (hour)

\_\_\_\_\_

Atrial Fibrillation at discharge

- Yes
- No

Treatment for A Fib

- None
- Amiodarone IV
- Amiodarone Oral
- Cardioversion (inc chemical CV)
- Rhythm device (pacemaker/ICD) placement
- Other

A Fib resolved at discharge

- Yes
- No

Bradycardia

- None
- Yes - not treated
- Yes - required pacing

Discharge Status

- Alive
- Dead

Discharge Date

\_\_\_\_\_  
(death date if patient died in hospital)

Atrila Fibrillation at 1 week

- Yes
- No

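### Section 14.1's exclude-and-replace rule, read with Sections 4.6.2 and 6.4, can remove gel-treated patients, including in-hospital deaths before AF, and it conflicts with other parts of the plan

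*Combined protocol and SAP*

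**What the plan says.** Section 14.1 sets two removal rules for the study arm. The first is "Patients who will dropout or withdraw from the study before reaching the primary end-point will be excluded from the study and replaced", with new enrolment to keep at least 20 patients. The second is "Subjects, who withdraw consent, will not be included in analyses", with no time limit. The sentence before these rules puts the endpoint analysis on an as-treated basis.

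Other sections decide whom the rules reach:

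- Section 4.6.2 counts a subject as enrolled once the study intervention has been given.
- Section 6.2.4 says of consented patients who become ineligible before surgery that "they will be considered a screen failure and will not undergo the study procedure".
- Section 6.4 gives an open list of withdrawal reasons. It includes non-compliance, termination by the investigator and "Subject is deceased (cause must be documented". It also provides for follow-up when withdrawal is due to a study-related adverse event.
- Section 9.3 lists the subject's death and withdrawal as separate ends of safety surveillance.
- The post-operative case report form has a discharge status of alive or dead. Its discharge date carries the note "death date if patient died in hospital".
- Section 4.5 says that all enrolled subjects, withdrawn ones included, "will be accounted for and documented".

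The primary endpoint is AF during the initial hospitalization. Thirty-day and one-year survival are secondary endpoints (Section 4.4.2). The primary objective in Section 4.3.1 begins "Demonstrate safety and effectiveness of the amiodarone hydrogel application".

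**The concern.** If enrolment happens at gel application, a withdrawal after enrolment is a patient who has been exposed. Replacing that patient removes an outcome after treatment and puts a different patient in its place. The historical controls come from records and cannot withdraw consent or be replaced under this rule, so the removal acts on one side of the comparison only.

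The most serious case is a gel recipient who dies in hospital without having had AF. Section 6.4 makes that a withdrawal, and Section 14.1 then excludes it. The patient would be lost to the survival endpoints as well as to the AF analysis, because the rule excludes from the study and not from a single endpoint. Deaths after AF or after discharge would stay in, so the distortion is partial, but on survival and safety it favours the gel. With 20 patients, one or two removals are visible in the results, and these results are meant to inform a larger randomised trial (Section 4.2).

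**Working it through.** The plan gives no figure for removals, dropout or mortality, so there is nothing to reproduce. The check has a textual part and an illustrative part.

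**1. Whom does the rule reach?**

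- Enrolled means gel applied (4.6.2). Patients found ineligible before surgery are screen failures (6.2.4).
- The cut-off in 14.1 is the primary endpoint, not gel application.
- Death, non-compliance and investigator termination are withdrawal reasons (6.4).
- Taken together, the interval between gel and discharge falls within the rule, and a death before AF in that interval can be excluded and replaced.
- The consent rule goes further. It also removes a patient who had AF and then withdrew consent.

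**2. What points the other way?**

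- An as-treated basis would keep gel recipients in.
- Section 9.3 treats death as distinct from withdrawal.
- The form's death date in the discharge field lets an in-hospital death count as completing the stay.
- A 30-day survival endpoint makes little sense if early AF-free deaths are removed.
- The Synopsis speaks of enrolment during the waiting period. Section 6.2.6 uses enrolment and withdrawal forms for patients who have not had the procedure.

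None of these limits 14.1 to patients before gel, and none says how death before AF is scored.

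**3. Survival, illustrated.** Assume 20 retained patients, all alive, and k removed deaths put back. Survival = 20/(20 + k), with exact (Clopper-Pearson) 95% limits.

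| k | Survival | 95% CI |
|---|---|---|
| 0 | 20/20 = 100% | 83.2 to 100 (lower limit 0.025^(1/20) = 0.832) |
| 1 | 20/21 = 95.2% | 76.2 to 99.9 |
| 2 | 20/22 = 90.9% | 70.8 to 98.9 |

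**4. AF rate, illustrated.** Restoring one patient changes x/20 to x/21 if AF-free, or to (x + 1)/21 if counted as an event.

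- AF-free: 2/20 = 10.0% becomes 2/21 = 9.5%. Removing AF-free deaths therefore works slightly against the gel on AF, by half a point here.
- Counted as an event: 0/20 = 0% becomes 1/21 = 4.8%; 1/20 = 5.0% becomes 2/21 = 9.5%; 2/20 = 10.0% becomes 3/21 = 14.3%. Each shift is between 4 and 5 points.

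**5. Tests, illustrated.** Section 4.2.3 gives 50 controls, and 14.1 gives a 30% AF rate and also speaks of 20 per arm. This yields 0.30 × 50 = 15 or 0.30 × 20 = 6 control events. Two-sided Fisher p, with the restored patient counted as an event:

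| Gel arm, before to after | v 15/50 | v 6/20 |
|---|---|---|
| 0/20 to 1/21 | 0.004 to 0.027 | 0.020 to 0.045 |
| 1/20 to 2/21 | 0.028 to 0.076 | 0.091 to 0.130 |
| 2/20 to 3/21 | 0.122 to 0.235 | 0.235 to 0.277 |

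Only one of the six cases crosses 0.05.

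**The case against.** The best defence is that the rule was meant to refill places lost before surgery. The Synopsis and Section 6.2.6 support this, since the plan completes withdrawal forms for patients who never had the procedure. The as-treated sentence, Section 9.3 and the survival endpoints also make it implausible that the authors meant to delete treated deaths. This stands as a likely intent. It does not stand as what the text says: 14.1 places its cut-off at the primary endpoint, and the sections give conflicting enrolment points.

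A second defence is that little is lost, because adverse events and deaths are recorded (Sections 9.3 and 10) and withdrawn patients are accounted for. That is true of collection. No section returns an excluded patient to the AF, survival or safety analyses, and no safety analysis set is defined.

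A third is that use of data after consent withdrawal may be governed by the consent form, which is not in the reviewed copy. That stands, and the remedy has to allow for it.

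A reader might infer three stronger things that the documents do not support:

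- *That the plan is silent on in-hospital death.* It is not. Section 6.4, Section 9.3 and the case report form each address it, in different directions. The gap is narrower: how death before AF is scored.
- *That removal of deaths is likely.* Any such probability needs an in-hospital mortality and a share of deaths that would be retained. The documents give neither.
- *That the rule decides statistical significance.* The crossing in step 5 is confined to 1/20 against 15/50, and 14.1 says that the size does not rest on a power analysis.

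**Conclusion.** The point holds as a conflict in the text that should be fixed. Followed literally, Section 14.1 with Sections 4.6.2 and 6.4 can remove and replace gel-treated patients, in the gel arm only, while other parts of the plan imply that they stay in. It does not show that the sponsor intends to drop deaths.

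Thirty-day and one-year survival and safety are the main exposure. The survival shift is 4.8 points for one restored death and 9.1 for two, with wide and overlapping intervals. For AF, one restored patient moves the rate by at most about 5 points. The larger shift arises only if that patient had AF or is counted as an event.

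These sizes rest on assumed counts: 20 retained survivors, 0 to 2 AF events in the gel arm, and 30% AF in controls. The frequency of removals is unknown. For deaths it is zero if an in-hospital death is meant to complete the index stay. Other removals before discharge should be few, because the gel is given once and outcomes come from records.

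**What to change.** In Section 14.1, state that:

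- every subject in whom gel was applied is analysed for AF, survival and safety, using data to discharge, death or withdrawal as far as consent allows;
- only consented subjects who never received gel are replaced;
- death is an outcome and not a withdrawal for analysis, with Section 6.4 aligned;
- death before AF is scored by one stated rule in the gel and control groups, with a sensitivity analysis that counts such patients as events.

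Report the number, timing and reasons of withdrawals after gel. Reconcile the enrolment point across the Synopsis (Data Collection) and Sections 4.6.2, 6.2.6 and 9.3.

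The cost is mainly wording. The plan already provides for collecting the gel-arm data. Control death and discharge data would have to be extracted in the same way, and gel-arm results may look slightly less favourable. If replacement was always meant for patients who never received gel, that part of the change only makes the intent explicit.

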We aim to study the intraoperative application of an amiodarone containing hydrogel for prevention of post-operative atrial fibrillation in lung transplant patients.

In patients undergoing lung transplantation, post-operative atrial fibrillation is common and leads to prolonged hospital course and increased healthcare expenditures. Amiodarone is a main stay of therapy for atrial fibrillation, however this drug does have potential serious complications when administered systemically. The local application of amiodarone, could potentially decrease the rates of atrial fibrillation, while avoiding the systemic complications. This has the potential to decrease length of stay and decrease additional procedures (ie. Cardioversion) in patients undergoing lung transplantation.

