#### **4.4.2 Secondary Endpoints**

- Length of Stay
- Development of post-operative atrial fibrillation during first year post transplant
- Thirty-day survival
- One-year Survival

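### At 20 gel patients v 50 historical controls, means such as length of stay should be compared by Welch's t-test; Student's t-test gives the wrong standard error if spreads differ (minor)

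*Combined protocol and SAP*

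**What the plan says.** Section 14.1 sets one rule for every continuous variable: "continuous variables will be tested using unpaired Student’s t-test or Wilcoxon rank-sum test, depending on variable distribution". It names no unequal-variance form. It promises means, medians and 95% confidence intervals, but does not say which contrast is the target for length of stay, and it states no significance level.

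Section 4.4.2 lists "Length of Stay" as a secondary endpoint, and ICU duration is collected under 4.2.2. Section 2.0 gives the reason for interest in stay: "This has the potential to decrease length of stay and decrease additional procedures (ie. Cardioversion) in patients undergoing lung transplantation".

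On group sizes, section 4.2.3 says "Enrollment will include at least 20 patients undergoing lung transplant" and sets 50 historical controls. Section 14.1 instead remarks that "a sample size of 20 in each arm may have sufficient power to answer the question of preliminary effectiveness and safety". It also says that the sample size does not rest on a power analysis.

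**The concern.** Student's t-test estimates one common variance from both groups. With equal group sizes this does little harm when the true variances differ. With 20 v 50, the pooled variance is dominated by the larger group, while the true variance of the difference is dominated by the smaller one. If the 50 controls are the more variable, the standard error is too large: the interval is too wide and a real saving in days is easier to miss. If the 20 gel patients are the more variable, it is too small, and the test rejects too often.

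The plan's own reasoning makes equal spread doubtful if the gel works. It says "the reported rate of early atrial fibrillation post lung transplantation is approximately 30" per cent, that AF lengthens stay, and it sizes the study "assuming that the use of amiodarone gel will result in prevention of atrial fibrillation in 90% patients". Preventing AF would remove long stays from the gel group only. The controls may also date back to 2005 (section 4.2), so their spread may differ for reasons unrelated to the gel.

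At stake are the length and error rate of the interval for a secondary endpoint in a pilot that is meant to inform a larger randomized trial.

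**Working it through.** The plan gives no figure for length of stay (no SD, difference or power), so there is none to reproduce.

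**Inputs from the documents.** 20 gel v 50 controls (4.2.3). Control AF rate 30% (14.1). Gel AF rate 10% if the 90% means AF-free patients, or 3% if it means a 90% relative reduction (14.1 can be read either way).

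**Assumed.** Two-sided 5% level, and all spreads.

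**Step 1: error of the pooled standard error.** Set the control SD to 1 and the gel SD to r.

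- True variance of the difference: V = r²/20 + 1/50.
- Expected pooled variance: P = [(19r² + 49)/68] × (1/20 + 1/50) = [(19r² + 49)/68] × 0.07.
- Approximate rejection rate at equal means: 2[1 − Φ(t × √(P/V))], with t = 1.9955 on 68 degrees of freedom.

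At r = 2: V = 0.2200, P = (125/68) × 0.07 = 0.1287, √(V/P) = 1.31, rate about 12.7%. At r = 0.5: V = 0.0325, P = (53.75/68) × 0.07 = 0.0553, √(V/P) = 0.77, rate about 0.9%.

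Simulation with normal data and equal means (60,000 replicates; 20,000 at r = 0.67):

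| Gel/control SD ratio | Student | Welch |
|---|---|---|
| 0.5 | 1.2% | 5.1% |
| 0.67 | 1.9% | 4.6% |
| 1 | 4.9% | 4.9% |
| 1.5 | 9.8% | 5.0% |
| 2 | 13.3% | 5.0% |

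Error therefore passes 10% only when the gel SD is about 1.5 to 1.6 times the control SD or more.

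**Step 2: which ratio the plan's mechanism implies.** Assume a lognormal base stay with median 14 days and log-SD s, and that AF adds d days with probability p. Then SD² = 196·exp(s²)·[exp(s²) − 1] + p(1 − p)d².

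- s = 0.3, d = 14: control 20.2 + 0.21 × 196 = 61.4 (SD 7.83). Gel at 3% AF: 20.2 + 0.0291 × 196 = 25.9 (SD 5.09). Ratio 0.65.
- s = 0.8, d = 7: control 333.2 + 0.21 × 49 = 343.5 (SD 18.53). Gel at 10% AF: 333.2 + 0.09 × 49 = 337.6 (SD 18.38). Ratio 0.99.

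**Step 3: power in these cases at 20 v 50** (40,000 simulated replicates each):

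| s | Days added by AF | Gel AF | SD ratio | Student | Welch | Wilcoxon |
|---|---|---|---|---|---|---|
| 0.3 | 7 | 10% | 0.90 | 15% | 20% | 15% |
| 0.3 | 7 | 3% | 0.84 | 25% | 32% | 25% |
| 0.3 | 14 | 10% | 0.79 | 28% | 37% | 23% |
| 0.3 | 14 | 3% | 0.65 | 51% | 64% | 39% |
| 0.5 | 7 | 10% | 0.96 | 8% | 12% | 10% |
| 0.5 | 7 | 3% | 0.94 | 12% | 17% | 15% |
| 0.5 | 14 | 10% | 0.89 | 17% | 23% | 17% |
| 0.5 | 14 | 3% | 0.83 | 28% | 37% | 28% |
| 0.8 | 7 | 10% | 0.99 | 5% | 9% | 8% |
| 0.8 | 7 | 3% | 0.99 | 6% | 11% | 10% |
| 0.8 | 14 | 10% | 0.97 | 8% | 14% | 12% |
| 0.8 | 14 | 3% | 0.95 | 12% | 20% | 18% |

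Before rounding, Welch's gain over Student is 3.8 to 14.0 points. Where the ratio is close to 1, the gain comes largely from skewness, not from unequal variances. With 30% AF in both groups the stays have one common distribution, and all three tests reject about 5% of the time (Student 4.6 to 5.1%, Wilcoxon 4.7 to 4.9%, Welch 5.1 to 5.7%).

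**Step 4: dependence on group sizes.** At 20 v 20, P = [(r² + 1)/2] × (2/20) = (r² + 1)/20 = V for every r. In simulation the pooled test then rejects 5.0 to 5.4% for normal data and at most 6.9% in the lognormal cases run. In the 12 scenarios at 20 v 20, Student and Welch differ by less than 1 point of power.

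**Step 5: cost of Welch.** With equal SDs and a difference of 0.5 SD at 20 v 50, power is 45.9% for Student and 44.8% for Welch. For lognormal stays with equal means and a gel SD twice the control SD, Welch's error is 8 to 10%, against 13 to 14% for Student.

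**The case against.** The pooled form is inferred from the name of the test; 14.1 does not write it. This stands as a caveat, but it is the usual meaning, and nothing in the plan points to another.

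Section 14.1 speaks of 20 in each arm, where the fault nearly disappears. This stands in part. That sentence is a remark about power, while 4.2.3 sets the number of controls at 50, so the plan is inconsistent and the size of the point depends on which figure holds.

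The study is an expressly unpowered pilot. In 11 of the 12 scenarios Welch's power is only 9 to 37%, so most real savings would be missed with any test. This stands and limits the severity.

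Skewed stays may be sent to the Wilcoxon test anyway. That is possible. The point then applies to whatever means and intervals are still compared.

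Three stronger readings are tempting, and the documents do not support them:

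- *A reader might infer that false-positive error above 10% is to be expected.* It needs a gel group at least about 1.5 times as variable, and the plan's mechanism points the other way. If the gel does nothing and the groups are comparable, Student's t-test and Wilcoxon both hold about 5%.
- *A reader might infer that Student's t-test has the wrong null hypothesis.* It does test equal means, assuming equal variances. The fault lies in its standard error.
- *A reader might infer that Wilcoxon should be demoted because it does not test mean stay.* The plan names no mean-days target and reports medians too. A rank test for skewed stays is a conventional choice, and its rejections at equal means are errors only if the mean is the target.

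**Conclusion.** The point holds in a limited form and is minor. If means are compared at 20 v 50, the pooled standard error is miscalibrated whenever spreads differ, and Welch's is the better default. Under the plan's own mechanism the expected harm is an over-strict test, costing about 4 to 14 points of power in the assumed scenarios. Inflated error (about 10% at an SD ratio of 1.5, 13% at 2) is a possibility that non-concurrent controls leave open, not a prediction of the documents.

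The conclusion rests on reading Student's as pooled, on 50 controls, on a two-sided 5% level, and on assumed spreads and AF-related days, since the plan gives none.

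**What to change.** In 14.1, replace the unpaired Student's t-test with the Welch (unequal-variance, Satterthwaite) t-test. Report the matching 95% confidence interval for every between-group difference in means, including length of stay and ICU duration. Wilcoxon may stay as the rank-based analysis.

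Reconcile the control-group size between 4.2.3 (50) and 14.1 (20 in each arm), because the gain depends on it.

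The cost is one sentence and no new data, and the test can be run in the SAS release already named. About 1 point of power is lost if the SDs are equal. Welch's error stays above 5% for strongly skewed stays with a more variable gel group, reaching 13% in the most extreme lognormal case run (SD ratio 3; Student 20%). The change does not settle how in-hospital deaths count: the case report form in Appendix E enters the death date as the discharge date, so an early death shortens the recorded stay under any of these tests.
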